### **Confirmed influenza in association with protocol-defined ILI**

A subject is said to have a laboratory-confirmed influenza in association with protocol-defined ILI, if

- the subject had a protocol-defined ILI;
- the subject had a nasopharyngeal (NP) or nasal and throat swab; and
- the NP or nasal and throat swab was qRT-PCR- or culture-positive for influenza of any type.

A subject is said to have a culture-confirmed influenza in association with protocol-defined ILI if

- the subject had a protocol-defined ILI;
- the subject had a NP or nasal and throat swab; and
- the NP or nasal and throat swab was culture positive for influenza of any type.

Although the protocol required the nasal or throat swab to be performed during a window of 3 days post onset date, positive results from nasal or throat swabs obtained out of the window of 3 days will be used in the analysis and the subject will be considered as having laboratory confirmed influenza.

Number of subjects with missing swab results will be reported. The number of swabs performed out of the window of 3 days post onset date will be reported.

The time to onset and duration of the confirmed case of influenza with protocol-defined ILI will be identical to the time to onset and duration of the associated ILI episode.

## 5.2 Efficacy Assessment

The assessment of vaccine efficacy will be performed over one flu season and will focus on events which occurred during the flu season in cohorts 1 and 2. Given the surveillance plan, only events which occurred at least 14 days after the second vaccination will be captured.

### Primary efficacy assessment:

Vaccine efficacy (VE) against qRT-PCR- or culture-confirmed influenza illness is defined as  $VE = 1 - [p_V/p_P]$ , where  $p_V$  and  $p_P$  are the proportions of subjects with qRT-PCR- or culture-confirmed influenza caused by any influenza A or B virus in association with a protocol-defined Influenza-Like Illness (ILI) in the M-001 experimental and placebo groups, respectively.

### Secondary efficacy assessment:

1. Vaccine efficacy against culture-confirmed influenza illness, defined as  $VE^c = 1 - [p_V^c/p_P^c]$ , where  $p_V^c$  and  $p_P^c$  are the proportions of subjects with culture-confirmed influenza in association with a protocol-defined Influenza-Like Illness (ILI) in the M-001 experimental and placebo groups, respectively.
2. Average duration of the ILI episode or average number of days with respiratory or systemic symptoms during the first qRT-PCR- or culture-confirmed influenza illness episode in the M-001 experimental group and placebo group.
3. Proportion of subjects with ILI episodes in the M-001 experimental group and placebo group.

For the primary efficacy and secondary assessments 1 and 2 in case of multiple qRT-PCR- or culture-confirmed ILI events observed for the same subject, only the first qRT-PCR- or culture-confirmed ILI event will be considered. For the secondary assessment 3, the number of ILI episodes in the M-001 experimental group and placebo group will also be assessed.

### Exploratory efficacy assessments:

- Reduction, due to vaccination with M-001, in the proportion of subjects taking antibiotics due to a post-influenza respiratory tract infection (ILI with confirmation by viral culture or qRT-PCR analysis)
- Reduction, due to vaccination with M-001, in the proportion of subjects taking medications due to qRT-PCR- or culture-confirmed ILI

- Reduction, due to vaccination with M-001, in the number of hospitalizations associated with ILI with or without confirmation by viral culture or qRT-PCR analysis
- Reduction, due to vaccination with M-001, in the incidence of death due to ILI with or without confirmation by viral culture or qRT-PCR analysis
- Reduction in the proportion of subjects with serious ILI with or without confirmation by viral culture or qRT-PCR analysis

In addition to the above exploratory endpoints, the following exploratory subgroup analyses will be performed based on the first qRT-PCR- or culture-confirmed ILI event.

- VE against qRT-PCR-confirmed Type A influenza illness, VE against qRT-PCR-confirmed Type B influenza illness
- VE against qRT-PCR-confirmed Type A/H1N1 influenza illness
- VE against qRT-PCR-confirmed Type A/H3N2 influenza illness

#### Sensitivity analyses of primary efficacy assessment:

As a sensitivity analysis to the primary efficacy assessment, the time to first qRT-PCR- or culture-confirmed influenza in association with a protocol-defined ILI will be analyzed.

An additional sensitivity analysis to the primary efficacy assessment will be performed where qRT-PCR- or culture-confirmed influenza is defined if the qRT-PCR Ct count corresponding to the detection of any flu type is  $< 40$ .

### **5.3 Efficacy Analysis Populations**

The subjects with major and minor protocol deviations will be reported in the CSR.

Below is the list of major protocol deviations that lead to exclusion from the from PP set.

#### **Per-Protocol (PP) Set**

The primary efficacy analysis set (PP Set) will exclude

- Subjects who did not satisfy all protocol-specified inclusion criteria or met at least one exclusion criterion,
- Subjects who did not receive both doses of M-001/placebo as randomized,
- Subjects who did not receive M-001/placebo that was properly handled or was otherwise not acceptable for administration (unblinded subjects will be excluded),
- Subjects or their representative who were not contacted by the surveillance center, did not have any phone call, or any visit 15 days or more after second injection,

- Subjects who received a seasonal influenza vaccine between randomization and end of the surveillance period,
- Subjects who received a licensed live vaccine within 30 days of any dose of M-001/placebo that interfered with the evaluation of the investigational product, and
- Subjects who received a licensed non-live vaccine within 21 days of any dose of M-001/placebo that interfered with the evaluation of the investigational product.

Data from the database will be used to flag the protocol violations.

The results of the NP or nasal and throat swab collected outside of the allowed window following the ILI will be considered valid.

List of subjects excluded from the per-protocol analysis will be finalized prior to unblinding the database and described in the blinded data analysis memo.

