11.5.1. Analysis Populations

The Safety Analysis population includes all subjects who received at least one dose of study vaccine. Subjects in the safety population will be analyzed according to the treatment actually received.

The intent-to-treat (ITT) population includes all subjects who received at least one dose of study vaccine. Subjects in the ITT population will be analyzed according to their randomization.

The per protocol (PP) population includes all subjects in the ITT subset satisfying the following criteria:

- Subject met all protocol-specified inclusion criteria and met no exclusion criterion,
- Subject received both doses of M-001/placebo as randomized, in the protocol-specified time frame, and at the intended dose level,
- Subject did not receive M-001/placebo that was not properly handled or was otherwise not acceptable for administration,
- Subject had at least one successful surveillance contact 15 days or more after the second dose of M-001/placebo, or attended at least one ILI visit due to ILI symptoms
- Subject did not receive a seasonal influenza vaccine between randomization and end of the surveillance period for Season 1,
- Subject did not receive a licensed live vaccine within 30 days of any dose of M-001/placebo, and
- Subject did not receive a licensed non-live vaccine within 21 days of any dose of M-001/placebo.

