## **5.4 Efficacy Endpoints Analysis Methods**

### **5.4.1 Hypothesis**

The hypothesis to be tested is:  $H_0 : VE \leq 40\%$

where VE denotes the vaccine efficacy of M-001 against qRT-PCR- or culture-confirmed influenza in association with protocol-defined ILI over a first season of influenza.

The hypothesis will be rejected and the superiority of M-001 demonstrated if the lower bound of the two-sided 95% CI for VE is  $>40\%$  for the primary per-protocol analysis.

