## 11. CHANGES OF ANALYSIS FROM PROTOCOL

Protocol version 1.0

No lot consistency analysis will be performed in a subset of subjects from Cohort 2, since all lots needed for the entire study will be produced by Cytovance. Immunogenicity analyses to be performed in a subset of subjects from Cohort 2 will be defined in a separate document (SAP for immunogenicity analyses).

Protocol version 5.0 – Amendment 1

The following changes were made compared to the analyses described in the protocol.

- the ILI episode for which a nasal or throat swab was collected outside of the allowed window of 3 days post onset date will be considered as a qRT-PCR or culture confirmed ILI if the results of the qRT-PCR or culture were positive. Review of each case will be performed prior to unblinding and documentation provided in the blinded data review meeting memo (see section 5.3).
- the analysis of the secondary efficacy assessment consisting in the between-group comparison of the number of days with respiratory or systemic symptoms among subjects with qRT-PCR- or culture-confirmed influenza illness will be performed on the percentage of subjects with number of days with respiratory or systemic symptoms in the following categories:
  - < 7days
  - At least 7 and < 14 days
  - At least 14 and < 21 days
  - > 21 days

Cochran-Mantel-Haenszel test with 4 strata corresponding to the combination of age category and cohort will be used.

- these exploratory endpoints have been added :
  - Reduction, due to vaccination with M-001, in the proportion of subjects with serious ILI with or without confirmation by viral culture or qRT-PCR analysis
  - Reduction, due to vaccination with M-001, in the proportion of subjects taking medications due to qRT-PCR- or culture-confirmed ILI

In addition, more details are provided in the SAP compared to the protocol.

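### The SAP's per-protocol set, which decides the primary test, drops the protocol's dose-timing condition and qualifies its other-vaccine exclusions, and SAP section 11 does not say so.

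*SAP*

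**What the plan says.** SAP 5.4.1 ties rejection of the null hypothesis to the lower confidence bound "for the primary per-protocol analysis", so PP membership is part of the primary test.

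Protocol 11.5.1 sets this condition: "Subject received both doses of M-001/placebo as randomized, in the protocol-specified time frame, and at the intended dose level". SAP 5.3 introduces its own bullets with "Below is the list of major protocol deviations that lead to exclusion from the from PP set", and the matching bullet is "Subjects who did not receive both doses of M-001/placebo as randomized".

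On other vaccines, the protocol's live-vaccine condition is unqualified: "Subject did not receive a licensed live vaccine within 30 days of any dose of M-001/placebo, and" the next bullet sets the same kind of rule at 21 days for non-live vaccines. SAP 5.3 excludes only recipients of a live vaccine "within 30 days of any dose of M-001/placebo that interfered with the evaluation of the investigational product", and attaches the same qualifier to the non-live bullet. SAP 5.3 also adds that "unblinded subjects will be excluded", which protocol 11.5.1 does not have.

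SAP section 11 opens its entry for protocol version 5.0 with "The following changes were made compared to the analyses described in the protocol". It then lists the out-of-window swab rule, the symptom-duration categories with their test, and two added exploratory endpoints. The SAP overview of changes from SAP 1.0 says only that the PP exclusion criteria were clarified, in a list described as clarity or editorial updates.

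**The concern.** The protocol and the SAP give different membership rules for the set on which the trial succeeds or fails, and both cannot be followed. SAP 5.3 presents its bullets as the list of excluding deviations, so a condition missing from the list would not be applied.

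Off-window second doses are foreseen. Protocol 5.3.3 allows them with sponsor approval, and protocol 6.2 asks for the window only where possible. A subject dosed late is out of the PP set under the protocol and in it under the SAP.

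The interference qualifier replaces a date rule with a judgement. SAP 5.3 says that database data will flag violations, but no database field can settle whether a vaccine interfered unless somebody first defines it.

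A reader who turns to SAP section 11 for departures from the protocol would learn none of this. The planned ITT analysis does not isolate the effect, because it also brings in one-dose subjects and every other PP exclusion.

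**Working it through.** **1. The two texts, side by side**

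| Condition | Protocol 11.5.1 | SAP 5.3 | In SAP section 11? |
|---|---|---|---|
| Both doses as randomized | yes | yes | not applicable |
| Both doses within the time frame | yes | absent | no |
| Intended dose level | yes | absent | no |
| Live vaccine within 30 days | any | only if it interfered | no |
| Non-live vaccine within 21 days | any | only if it interfered | no |
| Unblinded subjects excluded | absent | added | no |

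Section 11 does declare the relaxation of the swab window, a change of the same kind. Its closing remark that the SAP gives more detail than the protocol does not describe conditions that were removed.

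**2. The window itself**

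The protocol synopsis, protocol 11.3.1 and SAP 3.4 print 21-30 days between doses. Protocol 7.2.1 prints 22 days plus 9 after the first vaccination day. Read literally, that is 22 to 22 + 9 = 31 elapsed days. With the vaccination day counted, as the protocol counts its safety reporting periods, it is 21 to 30. Restoring the criterion therefore needs one stated range.

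**3. The plan's own figure**

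Inputs from protocol 11.3.2 and SAP 5.4.2: 182 cases, 1:1 allocation, true VE 62%, success if the lower 95% bound exceeds 40%, one-sided level 0.025. With equal denominators the vaccine share of cases is q = (1 − VE)/(2 − VE).

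- At VE 40%: q = 0.6/1.6 = 0.375.
- At VE 62%: q = 0.38/1.38 = 0.2754.
- At 182 cases, 55 vaccine cases give a lower VE limit of 40.1% (success) and 56 give 38.6% (failure).
- Exact power at 182 cases is 81.5%, with actual one-sided level 0.0242. Averaged over 176 to 188 cases, power is 80.1%. The stated 80% is reproduced.
- Expected cases, reading 2.41% as the placebo rate: 12,000 × 0.9/2 × 0.0241 × 1.38 = 179.6, close to 182.

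**4. How often the two timing rules could disagree**

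The documents give no off-window rate. Assume that a fraction f of cases is off-window, independently of arm. Draw the vaccine cases from Bin(n, 0.38/1.38), drop each case with probability f, recompute the success boundary at the remaining n, and sum the probability that the two decisions differ. Protocol 11.3.2 and 11.3.3 place the 182 cases after PP exclusions, so the first version sets n = round(182/(1 − f)) under the SAP rule. The second version puts 182 under the SAP rule.

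| f (assumed) | n under SAP rule (expected under protocol rule) | Decisions differ | Decisions differ if n = 182 under SAP rule |
|---|---|---|---|
| 0.5% | 183 (182.1) | 1.1% | 1.8% |
| 1% | 184 (182.2) | 1.9% | 2.6% |
| 2% | 186 (182.3) | 3.0% | 3.6% |
| 5% | 192 (182.4) | 5.0% | 5.8% |

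The dose-level and other-vaccine differences cannot be sized from the documents.

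**The case against.** The strongest reply is that the SAP follows the protocol's own dosing rules. The interval is called recommended, the window applies where possible, and late dosing is allowed with sponsor approval, so keeping such subjects may be deliberate and sensible. That stands as a reason for the SAP's rule. It does not remove the time-frame condition from protocol 11.5.1 or explain the silence in section 11.

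Three further points stand and limit the weight.

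- Dose level is nearly empty as an issue. There is one dose of 1 mg with no dose modifications (protocol 6.2), in single-dose vials or prefilled syringes (protocol 6.1.1). The SAP also keeps the bullet on product not acceptable for administration, which may catch some draw-up errors.
- The interference qualifier reaches less than it seems to. The eligibility bullet still removes anyone who met exclusion criterion 3e (other vaccines within 30 days before, or planned during, the study), and seasonal influenza vaccine remains an unqualified exclusion. What is left is mainly unplanned, non-influenza vaccines after enrolment.
- The exclusion list is fixed before unblinding and described in a memo. Deviations are summarized by group, and Table 14.2.9.3 shows the dose intervals.

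A reader might infer that the criteria were loosened with knowledge of treatment, or to collect cases. The documents do not support that: the list is finalised blind, and nothing in them indicates such a motive.

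**Conclusion.** The conflict is real. Protocol 11.5.1 and SAP 5.3 define the primary PP set differently, chiefly on dose timing and on the qualified other-vaccine exclusions, and the difference is not declared. It should be fixed, because the primary population needs one definition and this one changes who enters it.

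The effect on the decision is small: about 1% to 6% of trials if 0.5% to 5% of cases are off-window, with true VE 62%, about 182 cases and off-window status unrelated to arm. A lower off-window rate gives a lower figure. It matters only for a result close to the 40% bound.

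Two stronger readings should be resisted. One is that the SAP's rule biases VE: under an arm-independent rate the expected VE is unchanged, and the documents give no reason to expect imbalance. The other is that power is lost: the planned 182 cases already stand after PP exclusions, so no loss is claimed. Nor is the 1% to 6% an estimate for this trial, since the off-window rate behind it is assumed.

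**What to change.** Before unblinding:

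- Restore the timing criterion in SAP 5.3 with one numeric window, 21-30 elapsed days between doses. The dose-level words can go back in the same line.
- Remove the interference qualifiers from the live and non-live vaccine bullets, so that dates in the database alone determine exclusion.
- If the sponsor means to keep off-window subjects, state that rule in SAP section 11 with its reason, and report the primary VE once under the protocol 11.5.1 definition.
- Record the added exclusion of unblinded subjects in section 11 as well.

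The cost is a few lines in SAP 5.3 or section 11 and, only if the SAP's rule is kept, one extra run of the primary table.

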Protocol defined ILI end date is the date when for at least 24 hours ILI symptoms are no longer present. Of note, some symptoms may persist after ILI for a long time, but the duration of ILI is to be determined by presence of symptoms of ILI understood as active disease, or “influenza symptom”, contrary to symptoms being part of an underlying chronic condition (e.g. COPD, arthritis), and contrary to chronic complications and/or sequelae of the ILI. When no clear end of ILI can be observed, the PI is requested to make rational judgment and determine the ILI end date based on available data and his/her experience. It is expected, that normally, ILI should not last longer than 2-3 weeks, and in case of suspected overlapping new infection, the two infection episodes should be recognized by PI as separate ILI cases.

Laboratory testing for the confirmation of influenza:

All NP/nasal and throat swab specimens will be submitted for analysis by polymerase chain reaction (qRT-PCR), and when the result is found positive, and if there is a sufficient content of viruses (as determined by Ct value ≤ 35)” [Ct= cycle threshold] another aliquot from such specimen will be also examined by culture confirmation test. Typing and subtyping of the influenza virus will be performed with PCR based method.

Optional test: Positive cultures samples will be stored and may undergo additional testing in the future (subtyping or strain identification, utilizing genetic sequencing and antigenic analysis using hemagglutination inhibition [HAI] against a panel of known standard ferret reference antisera to different viral strains) to further determine the breadth of protection provided by M-001.

Out of study influenza infection confirmation: in cases when no swab collection was performed within study framework, but valid, relevant external medical documentation exists confirming recent or ongoing influenza infection (laboratory confirmation – PCR, culture or serology - IgM antibodies), such medical documentation will be subject to sponsor’s approval as surrogate proofs of influenza infection, and if approved as valid, may be taken into account for exploratory analyzes. Details of exploratory analyzes will be defined in statistical analysis plan.

7.4. Safety Follow Up Visit, Visit 4, Day 202: Phone Call/ Electronic Communication (180 days [+/-14 days] post last study vaccination day)

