Subjects will be contacted by phone or electronic communication (e.g., email, text message) to query for safety events. In case follow-up contact is needed based on the responses, subjects will be asked to provide further details to the follow-up by phone. AEs limited to NOCIs and SAEs that have occurred since the previous visit will be solicited. Based on the information, subjects may be asked to return to the clinic for evaluation.

7.5. Follow Up Period for Efficacy Season 2

Passive surveillance will take place starting 14 days after the second injection and until May 15, 2020.

Active surveillance for cohort 2 will take place between December 1st, 2019 and March 31, 2020. During this period, the dedicated study staff will contact the participants up to twice a week to monitor for ILI symptoms as detailed above in 7.3. (Follow up calls in season 2019/20 will be for participants in cohort 2 only).

As of the end of the season 1, the follow up for Cohort 1 subjects in season 2019/2020 is not planned and participation of all Cohort 1 subjects will be assumed as completed with the end of Season 1, i.e. the latest on May 15th except for cases defined elsewhere (e.g. ongoing ILI, SAE follow-up).

7.6. Follow Up Period for Efficacy Season 3

Season 3 is not planned and is not encompassed by this study protocol.

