8.2.3. Special Assays or Procedures

Cellular (CMI) Studies

Assays to measure T cell responses will be performed by a qualified laboratory. Venous blood samples for isolation of PBMCs will be collected from a subset of cohort 2, immediately prior to the first study vaccination (Day 0, visit 1 in season 2), and approximately 15 days (day of the vaccination inclusive) after the second study vaccination (Day 36, visit 3, season 2).

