11.3. Sample Size Considerations

11.3.1. Study Design

This is a pivotal, multicentre, randomized, modified double-blind, placebo-controlled phase 3 trial to assess the safety and clinical efficacy of M-001, an influenza vaccine administered intramuscularly twice in older adults and the elderly (≥ 50 years of age). Subjects will be randomized 1:1 to vaccine or placebo with randomization stratified by cohort and age group. For season 2, stratification will also be performed for participation to the sub-study. All doses will be administered IM approximately 21 days apart (recommended window is 21-30 days). All subjects from cohort 1 will be followed for up to two consecutive influenza seasons with no obligation to continue in season 3 if the study is extended to third season with protocol amendment. It is not planned to extend the participation of the cohort 1 subjects beyond season 1. Subjects from cohort 2 will be followed up for one season. If the study is extended to third season with protocol amendment, it will be determined by the amendment if they are offered possibility to continue their participation in the next season and new, relevant consent will be then collected.

A total of up to 10 sites will be selected to participate to the CMI substudy. Blood samples will be collected prior to the first study vaccination (Day 0) and approximately 15 days (day of the vaccination inclusive) after the second vaccination (Day 36, 14 ± 2 days since day of the second vaccination) in 350 randomly chosen subset of subjects from these sites. M-001 subjects will be 3 times more likely to be selected in the subset than placebo subjects and T cell responses will be measured only in subjects who receive M-001.

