In cohort 2, immunogenicity testing is performed and includes performing CMI assays on blood samples obtained immediately at baseline (Day 0) and on samples collected on Visit 3 (referred to as Day 36, taking place 14±2 days since day of the administration of second dose of the vaccine/placebo). At sites participating in the CMI sub-study, data are obtained from a subset of approximately 263 participants randomly selected from the experimental group and from a subset of 87 participants randomly selected from the placebo group. Cell mediated immune responses to influenza antigens, including epitopes represented in the M-001 vaccine, are assessed at baseline (Day 0, before vaccination), and at 14±2 days since day of the administration of second dose of the vaccine/placebo (Day 36).

At least half of the participants will be ≥ 65 years of age.

Table 1: Schedule of Events (Season 1, 2018) (Cohort 1)

Study Visit (V)	01	02	04
Study Day	0	22	202 (Phone call or email)
Visit Windows		(+9)	(±14)
Consent process and Signed Consent Form 	X		
Assess eligibility	X	X	
Demographic data and Review Medical & flu vaccination History 	X	X	
Concomitant meds	X	X	
Vital signs	X		
Oral temperature	X	X	
Physical examination	X		
Randomization	X		
Review contraception/ Counseling 	X	X	
Pregnancy Test 	X	X	
Solicited/reactogenicity events assessment	X*	X*	
Unsolicited AEs/ Assessment	X#	X#	
NOCI, AESIs, SAE	X	X	X
Vaccination 	X	X	
Evaluate vaccination site	X	X	
Postvaccination procedures 	X	X	
Provision of Memory Aid	X	X	
Review of Memory Aid Data		X	

Interim report	End of Season 2018/19, June 2019
Collection of ILI symptoms through passive and active surveillance	
Passive Surveillance: Subjects will be instructed to contact the study site if they experience symptoms of a respiratory illness from Day 14 post-second vaccination day until 15 May the following year.
 
Active Surveillance: Between November 15, 2018 and March 31, 2019, the

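### SAP 5.3 lets any phone call or visit from Day 15 after dose 2 meet the per-protocol follow-up condition, where Protocol 11.5.1 asks for a surveillance contact or an ILI visit, and the SAP does not declare the change

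*SAP*

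**What the plan says.** Protocol 11.5.1 makes follow-up a condition of entry to the PP set: "Subject had at least one successful surveillance contact 15 days or more after the second dose of M-001/placebo, or attended at least one ILI visit" for ILI symptoms. SAP 5.3 turns this into an exclusion, removing subjects or representatives who were "not contacted by the surveillance center, did not have any phone call, or any visit 15 days or more after second injection". The restriction to surveillance contacts has gone.

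Two routine contacts fall after dose 2:

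- **Visit 4 (Protocol 7.4, both cohorts):** "Phone Call/ Electronic Communication (180 days [+/-14 days] post last study vaccination day". Its content is restricted: "AEs limited to NOCIs and SAEs that have occurred since the previous visit will be solicited".
- **Visit 3 (Protocol 7.2.2, all of cohort 2):** a site visit, or a phone call where a site visit is not feasible. SAP 3.4 describes it as "taking place 14±2 days since day of the administration of second dose". Protocol 11.3.1 calls the same time point "approximately 15 days (day of the vaccination inclusive) after the second vaccination".

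SAP 5.4.1 decides success on the PP analysis. SAP 5.4.2 estimates VE from cases divided by PP subjects, without person-time. The SAP's opening summary of changes says only that the PP criteria were clarified. Section 11, which lists departures from protocol version 5.0, does not mention them.

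The bullet just before the contact rule in SAP 5.3 reads "Subjects who did not receive M-001/placebo that was properly handled or was otherwise not acceptable for administration".

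**The concern.** The contact condition exists so that the primary denominator holds people whose influenza outcome was looked for. If a safety call meets it, a subject whom the surveillance team never reached counts as a full-season non-case unless they reported an illness themselves. This lowers the attack rates. It also distorts VE if such subjects are more common in one arm. Because the PP set decides the primary test, a loosening of its definition should be visible as a change from the protocol.

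The preceding bullet has a separate drafting fault. Read literally, the negation covers both limbs, so a recipient of product that was unacceptable for some other reason is not excluded. Protocol 11.5.1 excludes that subject.

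**Working it through.** **The plan's own figures.** Per-protocol subjects per arm: 12,000 × 0.90 / 2 = 5,400. Reading the 2.41% attack rate as the placebo rate, with true VE 62%, expected cases = 5,400 × 0.0241 × (1 + 0.38) = 179.6, against 182 stated. With 182 cases the exact conditional test has null share 0.6/1.6 = 0.375 and alternative share 0.38/1.38 = 0.2754. The lower limit exceeds 40% when at most 55 cases are on vaccine. This gives one-sided error 0.0242 and power 81.5%, against 80% stated. The design figures reproduce.

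**Which routine contacts meet the SAP rule.**

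- Visit 4 at 180 ± 14 days is Day 166 to 194 after the last dose, so a phone call always passes the 15-day limit. A call at that point cannot establish by swab an influenza illness from earlier in the season. An email-only contact is not a phone call, and the SAP does not say whether it is a visit.
- Visit 3 at 14 ± 2 days is Day 12 to 16. Days 15 and 16 pass, which is two of five. If the vaccination day is counted, Day 14 passes too, making three of five. Days 12 and 13 fail either way. Surveillance starts on Day 14, so a qualifying Visit 3 covers at most about two days of it.

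**Effect on VE.** Let uV and uP be the shares of each PP arm with no surveillance contact. Let a be the fraction of their influenza cases still found through self-report. Assume a is the same in both arms and that these subjects carry the same risk as others. Then

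observed VE = 1 − (1 − VE) × [1 − (1 − a)uV] / [1 − (1 − a)uP].

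The documents give none of uV, uP or a. With a = 0, the extreme case:

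| uV / uP | True VE 40% | True VE 62% |
|---|---|---|
| 5% / 5% | 40.0% | 62.0% |
| 4% / 2% | 1 − 0.6 × 0.96/0.98 = 41.2% | 62.8% |
| 5% / 2% | 1 − 0.6 × 0.95/0.98 = 41.8% | 63.2% |
| 2% / 5% | 1 − 0.6 × 0.98/0.95 = 38.1% | 1 − 0.38 × 0.98/0.95 = 60.8% |

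At 5% / 2% and a = 0 the one-sided error with 182 cases rises from 0.0242 to 0.038. With a = 0.5 the same pair gives 1 − 0.6 × 0.975/0.99 = 40.9%. With a = 1 it gives 40.0%. The a = 0 figures are therefore upper bounds on the shift.

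**Equal shares.** VE and its interval do not move. In an example of 50 vaccine and 132 placebo cases in 5,400 per arm, VE is 62.1% (47.2% to 73.2%) with or without 5% of each arm removed. Only the placebo attack rate changes, from 132/5,400 = 2.44% to 132/5,130 = 2.57%.

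**Whether another analysis repairs it.** The Cox sensitivity analysis in SAP 5.4.2 censors at the last successful contact of any kind, so a Day 202 call can credit an event-free season. That section provides for subjects without surveillance contact only in the ITT analysis (censored at day 1), as if the PP set held none.

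**The case against.** A reader might infer that these subjects were never surveilled and could not become cases. The documents do not support that. Protocol 7.3 tells every subject to report respiratory illness or ILI from Day 14 after dose 2 until 15 May, and a qualifying report leads to a swab within the swab-collection period. The accurate description is subjects with no surveillance contact, followed by self-report only.

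The group is also likely to be small. The SAP plans twice-weekly calls for months (the protocol says up to twice weekly in season 2). A subject must have missed all of these yet taken the Day 202 call or attended Visit 3 on a qualifying day. Visit 3 is the weaker route: it passes on only part of its window, and because it reviews interim medical history, the documents do not show that illness would go unasked there. Nor is this a cohort 2 problem alone, since the Day 202 route exists in both cohorts.

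Safeguards exist. SAP 8.3 and Tables 14.2.11.1 and 14.2.11.2 summarise days under active surveillance separately from days to last contact, by group in the PP set. Exclusions are fixed before unblinding, an ITT analysis supports the result, and subjects and assessors are blinded, so a difference between arms has no obvious cause.

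These arguments reduce the likely size. They do not remove the conflict between the two definitions. The tables would help show an imbalance but would not correct the set.

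The SAP bullet could also be read as excluding anyone who lacks any one of the three kinds of contact. SAP 8.3 treats call, phone contact and visit as alternatives, so the permissive reading is the natural one.

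**Conclusion.** The point stands as an undeclared loosening of the primary analysis set. It follows from the text alone and does not depend on any assumed fraction. Its numerical effect is modest and conditional: none on VE when the share without surveillance contact is equal by arm, and at most about 1 to 2 points in either direction for arm differences of 2 to 3 points.

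A reader might infer that the primary VE is biased upward. The documents give no share by arm and no reason to expect more such subjects on vaccine, so neither the existence nor the direction of a bias is shown. Any events lost because people were not reached are a follow-up loss, which changing the definition does not recover.

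The handling bullet is a wording slip whose intent is clear from the protocol. It needs correcting but adds nothing to the size of the main point.

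**What to change.** Before the PP exclusion list is finalised:

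1. Restore the Protocol 11.5.1 condition in SAP 5.3: exclude subjects who have neither a successful surveillance contact on Day 15 or later after dose 2 nor an ILI visit.
2. State that Visit 3 or Visit 4 alone is not a surveillance contact, and whether the vaccination day counts towards the 15 days.
3. Tabulate by arm the subjects this removes.
4. Reword the preceding bullet so that it excludes anyone given product that was mishandled or otherwise unfit for use, as the protocol does.

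The cost is SAP wording, one derived flag, one table and slightly fewer PP subjects. Cases should stay in through the ILI-visit limb, provided their swabs were taken at such a visit. That limb keeps self-reporters while dropping uncontacted subjects who stayed well, so it depends partly on outcome. The effect nearly cancels in VE when the shares are equal, and the table by arm shows whether it could matter. The restored rule still needs only one surveillance contact and does not ensure season-long follow-up.
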